11. MEASUREMENT OF EFFECT

This study only uses laboratory-based endpoints to measure the effect of AMR101 treatment. There are no clinically observable metrics that will be used as a primary or secondary endpoint or primary or secondary effect measure in this study. The primary efficacy endpoint is EPA levels in mucosal tissue. A detailed discussion of laboratory endpoints is included in section 9.

12. DATA REPORTING / REGULATORY REQUIREMENTS

Adverse event lists, guidelines, and instructions for AE reporting can be found in Section 7.0 (Adverse Events: List and Reporting Requirements).

12.1 Data Reporting

12.1.1 Method

The Primary Investigator and the study team will collect, manage, and perform quality checks on the data for this study using RedCap.

12.1.2 Responsibility for Data Submission

N/A

12.2 Data Safety Monitoring

The Primary Investigator and the study team will regularly review and monitor toxicity and accrual data from this study. The study team is composed of GI physicians, study coordinators, pharmacists and biostatisticians with direct experience in cancer clinical research. Information that raises any questions about participant safety will be addressed with the IRB.

The Primary Investigator will review study protocol periodically throughout the duration of the study for quality, validity and integrity assurance. Information to be provided to the Primary Investigator may include: up-to-date participant accrual; current dose level information; DLT information; all grade 2 or higher unexpected adverse events that have been reported; summary of all deaths occurring within 30 days of intervention for Phase I or II protocols; for gene therapy protocols, summary of all deaths while being treated and during active follow-up; any response information; audit results, and a summary provided by the study team. Other information (e.g. scans, laboratory values) will be provided upon request.

12.3 Multicenter Guidelines

N/A

12.4 Collaborative Agreements Language

N/A

13. STATISTICAL CONSIDERATIONS

This study is a single-arm clinical trial that will measure the effects of EPA treatment on specific biomarkers related to EPA incorporation, gut microbiota, gut metabolome, and immune response. In doing so, we aim to provide causality for the microbial and immune mechanisms that potentially mediate the beneficial effect of EPA for colorectal cancer prevention. We and others have put forth considerable effort to determine measurable biomarkers implicated in colorectal carcinogenesis. A comprehensive discussion of these biomarkers and their significance is provided in Section 9.

We will recruit 80 participants who recently underwent removal of their adenomatous polyps at MGH to conduct a single-arm trial of EPA (AMR101, 4 g/day) treatment for 2 months. The rationale for selection of this EPA preparation is because it 1) is FDA approved; 2) has good comparability across production lots; 3) has been previously used in several trials of EPA.^{111,132} The rationale for selection of this dose is because it is 1) the prescription dose approved by FDA; 2) consistent with other RCTs of EPA in colorectal neoplasia;^{13,120,133} and 3) can provide the best balance of efficacy and safety.

13.1 Study Design/Endpoints

This study is a single-arm trial of EPA treatment in patients with a history of colorectal adenoma.

The single-arm design is chosen for the following reasons: 1) Based on our prior experience, short-term dietary supplementation is unlikely to lead to substantial changes in lifestyle. 2) Any major lifestyle changes will be documented by the detailed lifestyle questionnaires and nutritional surveys administered at both the baseline (pre-intervention) and final (post-intervention) visits to allow for statistical adjustment in the analysis. Moreover, as described in the protocol, we will measure EPA content in red blood cells to further assess compliance and changes in omega-3 fatty acid intake. 3) Given the high dose (4 g/day) of highly purified and specially formulated omega-3 fatty acid used in the study (AMR101), even modest changes in lifestyle is unlikely to introduce significant confounding on the intervention effect of interest. For example, one serving (3 oz.) of Atlantic salmon only contains 1-2g of marine omega-3 fatty acids, and individuals have to consume at least 3 servings of salmon per day to achieve the intervention dose used in the study. 4) Given the fishy odor and oily appearance of the study drug, our MGH Research Pharmacy is unable to provide a visually identical, blinded placebo capsule for the study drug. Therefore, given all of these considerations as well as the biomarker-based nature of the study, we believe that the single-arm design is the best use of the limited resources for the study.

The primary aim is to assess the effect of AMR101 treatment on our primary efficacy endpoint, mucosal tissue EPA. A detailed discussion of the background of this biomarker is provided in Section 9.1.1.1. Briefly, we will determine the effect of AMR101 at standard dose on mucosal tissue EPA content through pre- and post-treatment comparison. The rationale for selection of this primary endpoint is to specifically test the effect of EPA on colonic tissue, which will build the mechanistic foundation for testing downstream endpoints within the local environment. Additional endpoints will include the gut microbiome, metabolome, urinary PGE-M and gene expression profile of mucosal tissue. Our study design for each of these endpoints is comprehensively discussed in Section 9. Statistical considerations relating to these endpoints are provided in the following sections.

13.2 Sample Size, Accrual Rate and Study Duration

Patients will be accrued in one stage with no early stopping rules. The total sample size is 80 patients and we expect accrual to be 6-7 participants per month and complete the enrollment process within one year. This accrual rate is based upon accruals under our recently completed IRB-approved protocol (Protocol # 14-496; [name], PI) for a similar trial of aspirin in patients with history of colorectal adenoma. Each patient will be followed for at minimum 8 weeks and at maximum 12 weeks. This total sample size accounts for participant drop out, as endoscopy studies typical experience a drop-out rate of approximately 10%.

The sample size is based upon the primary efficacy endpoint of M3PUFA supplement at 4 g/d increasing mucosal MO3PUFA composition from pre- to post-treatment period by a mean of 3.0%, according to previous studies.^{13,134} The null hypothesis is $H_0: \Delta_{\text{post}} - \Delta_{\text{pre}} = 0$ versus $H_A: \Delta_{\text{post}} - \Delta_{\text{pre}} \neq 0$, where Δ_{pre} and Δ_{post} are the measurement of mucosal MO3PUFA composition before and after the intervention, respectively. Based on prior studies, we assume the standard deviation (SD) of 9.0% for the paired difference in MO3PUFA measurement. With 80% power and the significance level of 0.05 in a two-sided paired t-test, we will require 73 participants to detect the mean change of 3.0% in MO3PUFA level from pre- to post-treatment period. To account for possible drop out

at 10%, we plan to enroll 80 patients.

Our accrual target rates for ethnic and racial minorities will likely be consistent with the rate at which we see these minorities in the gastroenterology practice at MGH. (See table on next page)

Accrual Targets				
Ethnic Category	Sex/Gender			
	Females		Males	Total
Hispanic or Latino	4	+	4	= 8
Not Hispanic or Latino	36	+	36	= 72
Ethnic Category: Total of all subjects	40	+	40	= 80
Racial Category				
American Indian or Alaskan Native	1	+	1	= 2
Asian	2	+	2	= 4
Black or African American	4	+	4	= 8
Native Hawaiian or other Pacific Islander	1	+	1	= 2
White	32	+	32	= 64
Racial Category: Total of all subjects	40	+	40	= 80

13.3 Stratification Factors

N/A

13.4 Interim Monitoring Plan

N/A

13.5 Analysis of Primary Endpoints

Analysis of mucosal tissue EPA (primary endpoint): Our primary biostatistician, [name], will supervise statistical analyses assessing the change in EPA levels in mucosal tissue after AMR101 treatment, using a paired t-test. In secondary analyses, we will use mixed linear regression models to adjust for duration of treatment and other major factors that may influence the gut microbiome, including aspirin use, antibiotic use, and major dietary and lifestyle patterns (e.g., fiber intake, physical activity, body mass index, smoking, and alcohol intake). A robust variance estimate will be used to eliminate any normality assumptions for the residuals.

13.6 Analysis of Secondary Endpoints

Microbiome analysis: [name] will supervise the gut microbiome analysis. Stool specimens collected before and after treatment will undergo metagenomics and metatranscriptomics sequencing to assess the influence of EPA intervention on the gut microbial

composition and function. We will use the computational tools developed by [name], a leading authority in microbiome data analysis (<http://[name].sph.harvard.edu/biobakery>). We will associate treatment status with the microbial operational taxonomic units (OTUs) determined by MetaPhlAn¹³⁵ using biomarker discovery tests: LEfSe (Linear Discriminant Analysis Effect Size),¹³⁶ a univariate class comparison method; and MaAsLin (Multivariate Analysis by Linear models),¹³⁷ a multivariate test that finds associations between clinical metadata and microbial abundance or function after adjusting for other covariates. Metatranscriptomic data will be analyzed using HUM¹³⁸AnN,¹³⁹ a software package designed to efficiently and accurately define the abundance of microbial pathways within the community, and then linked to treatment status by linear mixed effects model. We expect to find that, after EPA treatment, study participants will have increased gut bacterial diversity, experience beneficial changes in microbiota composition, and demonstrate decreased transcriptional activity of inflammatory pathways that have been previously correlated with an increased risk of colon cancer.

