1.3 Secondary Objectives

To measure the effect of EPA treatment on the gut microbiome and metabolome, urinary prostaglandin metabolites (PGE-M) and gene expression profile of colorectal tissue among individuals with a history of colorectal adenoma.

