9.1.5 Gut microbiome analysis

We will perform metagenomic and metatranscriptomic sequencing of microbial DNA and RNA on pre- and post-treatment stool samples to examine the biomolecular mechanisms by which gut microbial activity may be altered or respond to AMR101 treatment. Stool samples will be sent, coded, to the Broad Institute for processing and analysis.

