9.1.5.1 Collection of Biospecimens

Stool will be collected using a Roth net or aspirated through the endoscope during flexible sigmoidoscopy at both the initial and final visit.

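### The taxon-level microbiome analysis in 13.6 names no pairing and no participant term, although each evaluable participant gives one stool sample before and one after treatment

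*Combined protocol and SAP*

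**What the plan says.** The secondary objectives (1.3) include: "To measure the effect of EPA treatment on the gut microbiome and metabolome". Section 9.1.5 plans "metagenomic and metatranscriptomic sequencing of microbial DNA and RNA on pre- and post-treatment stool samples". Section 9.1.5.1 has the stool collected by Roth net or "aspirated through the endoscope during flexible sigmoidoscopy at both the initial and final visit". Section 13.7 excludes from all analyses anyone who does not return for the final sampling, so evaluable participants are meant to contribute both samples.

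For taxa, 13.6 says: "We will associate treatment status with the microbial operational taxonomic units (OTUs) determined by" MetaPhlAn. The tests named are LEfSe and MaAsLin: "a univariate class comparison method; and MaAsLin (Multivariate Analysis by Linear models". MaAsLin is described as "a multivariate test that finds associations between clinical metadata and microbial abundance or function after adjusting for other covariates". The covariates are not listed there. No pairing, blocking or participant effect is mentioned for either tool.

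Neighbouring analyses are more explicit. Metatranscriptomic data are summarised as "abundance of microbial pathways within the community, and then linked to treatment status by linear mixed effects model". Tissue EPA (13.5) has a paired t-test. Stool metabolites (13.6) have a paired t-test followed by a linear mixed effects model.

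**The concern.** The trial has one arm, so treatment status for a stool sample is simply the visit at which it was taken. The contrast is within person. A class comparison, taken at its plain meaning, sets a group of pre-treatment samples against a group of post-treatment samples and does not use the link between the two samples from one person. If abundances are positively correlated within person, the standard error it works with is too large.

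Section 13.6 expects that participants will "experience beneficial changes in microbiota composition". If the test that delivers the taxon list ignores pairing, real shifts can be missed for a reason unrelated to the drug. A short list would then partly reflect the choice of test.

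**Working it through.** **What the plan gives.** It states no power, alpha or sample size for taxa, so there is no taxon figure to reproduce. The only sample size (13.2) is for the primary endpoint: mean change 3.0, SD of the paired difference 9.0, two-sided 0.05, power 0.80. The normal approximation is ((1.960 + 0.842) × 9/3)² = 70.7, or 71. The exact paired t calculation gives 73, as stated. That calculation is already paired and is untouched by this point.

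**Inputs for the illustration.**
- Pairs: 80 enrolled less 10% drop-out (13.2) = 72.
- Test level: two-sided 0.05 for a single taxon (assumed).
- Shift d, in SDs of abundance at one visit, and within-person correlation ρ: not in the documents, so a range is shown.

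**Formula.** With unit SD at each visit, the true standard error of the mean difference is √(2(1−ρ)/n). An unpaired test uses √(2/n). Its effective critical value is therefore 1.96/√(1−ρ).

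At ρ = 0.5:
- Effective critical value 1.96/√0.5 = 2.77, so the actual two-sided level is about 0.006 instead of 0.05.
- d = 0.3: 0.3/√(1/72) = 2.55. Paired power is Φ(2.55 − 1.96) = 0.72; unpaired is Φ(2.55 − 2.77) = 0.41.
- d = 0.4: 0.4/√(1/72) = 3.39. Paired power is Φ(3.39 − 1.96) = 0.92; unpaired is Φ(3.39 − 2.77) = 0.73.

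**Simulation.** Normal data, 72 pairs, 5,000 trials per cell. A generic two-sample rank test stands in for an unpaired class comparison. Entries are unpaired v Wilcoxon signed-rank.

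| Shift (SD) | ρ = 0 | ρ = 0.3 | ρ = 0.5 | ρ = 0.8 |
|---|---|---|---|---|
| 0 (null) | 0.047 v 0.044 | 0.018 v 0.041 | 0.007 v 0.050 | 0.000 v 0.055 |
| 0.2 | 0.21 v 0.21 | 0.18 v 0.29 | 0.14 v 0.36 | 0.05 v 0.74 |
| 0.3 | 0.42 v 0.41 | 0.40 v 0.54 | 0.37 v 0.69 | 0.35 v 0.97 |
| 0.4 | 0.64 v 0.65 | 0.66 v 0.78 | 0.69 v 0.90 | 0.78 v 1.00 |
| 0.6 | 0.94 v 0.93 | 0.96 v 0.99 | 0.98 v 1.00 | 1.00 v 1.00 |

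The pattern matches the formula: no loss at ρ = 0, a clear loss for moderate shifts at positive ρ, and little loss once the shift is large.

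**Zero-heavy data.** With skewed abundances, half the baseline values at zero and latent correlation 0.5, the direction is the same: 0.32 v 0.57 at 0.3 SD and 0.61 v 0.82 at 0.4 SD. Scale matters for a mean-based paired test here: at 0.3 SD its power is about 0.58 on log(abundance + 0.5) but 0.47 on untransformed abundance.

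**A covariate to avoid.** The factors in 13.5 begin with duration of treatment. If duration D is coded 0 at baseline and 8 to 12 weeks at the final visit, the visit effect is the intercept of a regression of within-person change on D. Its standard error grows by √(1 + mean(D)²/var(D)). With D assumed uniform on 8 to 12 weeks, this is √(1 + 100/1.333) = √76 = 8.7. Averaged over random samples of 72 it is about 8.8. Duration so coded is nearly collinear with visit.

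**The case against.** The strongest reply is that the harm depends on a choice the plan has not made. A reader might infer that the plan commits to an unpaired analysis of taxa. The documents do not support that: MaAsLin is described only as a covariate-adjusting linear model, and a participant term is neither included nor ruled out. The illustration also uses a generic rank test, not LEfSe itself with its discriminant step, nor MaAsLin. This stands, and it limits the point to what is unstated, plus the plain reading of a class comparison.

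A reader might also infer a risk of spurious taxa. The arithmetic shows the opposite: with positive correlation the unpaired test rejects too rarely under the null.

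Next, these are discovery analyses, and a univariate screen followed by an adjusted model is an ordinary sequence. That is fair, and it keeps the grade low. It does not remove the gap, since the microbiome is a stated secondary objective with an expected result.

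Pairing does not rescue every null result either. At 0.3 SD and correlation 0.5, the signed-rank test still misses about 31% of true shifts (1 − 0.69). The plan nowhere proposes to infer absence of effect from a short list.

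Finally, the simulated paired test is the signed-rank, not a mixed model. With complete pairs, no covariates and positive estimated participant variance, the mixed-model visit effect is the mean within-person change, so the paired normal figures above (0.72 and 0.92) describe it approximately.

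It would also be tempting to widen the point to the unlisted covariates in 13.6, or to the absence of a stated false-discovery rule for taxa. Those are missing detail and are not part of this conclusion.

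**Conclusion.** The point holds as a minor one. For taxa, 13.6 names a class comparison and a covariate-adjusted linear model, and states no pairing or participant term for data that are paired by design. The mixed model in the same section is tied to pathways, and the paired tests elsewhere belong to tissue EPA and metabolites, so no other section fills the gap.

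If the visits are compared as independent groups, moderate shifts are detected less often: roughly half as often at 0.3 SD and correlation 0.5, with the loss vanishing at correlation 0 and shrinking for large shifts. These sizes rest on an assumed shift, an assumed correlation, a single test at 0.05 and a stand-in rank test.

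**What to change.** State in 13.6 that the inferential test for each taxon is a linear mixed model: MaAsLin with a participant random effect or, if the version used does not take one, an equivalent model. Specify:
- abundance on a transformed scale, with the transformation and the handling of zeros named in advance;
- visit (pre/post) as fixed effect and participant as random effect;
- the time-varying factors already listed in 13.5, leaving out duration of treatment coded as 0 at baseline;
- a Wilcoxon signed-rank test on within-person change as sensitivity analysis;
- LEfSe as descriptive.

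The cost is a few sentences of SAP wording and slightly more analysis work, with no new samples or assays. The model type is the one 13.6 already uses for pathways. The downside is that pairing gains nothing, or loses very slightly, if within-person correlation is near zero.

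### The planned metatranscriptomic model has no term for matched DNA, so it cannot separate lower transcription per copy from fewer carrier bacteria

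*Combined protocol and SAP*

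**What the plan says.** **Assays.** Section 9.1.5 states: "We will perform metagenomic and metatranscriptomic sequencing of microbial DNA and RNA on pre- and post-treatment stool samples". DNA and RNA are therefore both planned at both time points.

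**Model.** Section 13.6 processes the metatranscriptomic data with HUMAnN to "define the abundance of microbial pathways within the community, and then linked to treatment status by linear mixed effects model". It names no RNA/DNA ratio, DNA covariate, offset or other gene-copy normalisation. The only adjustment named in the microbiome paragraph belongs to MaAsLin, described as "a multivariate test that finds associations between clinical metadata and microbial abundance or function after adjusting for other covariates". Those covariates are not listed.

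**Expected findings.** The paragraph ends with two expectations for the same participants. One is compositional: "study participants will have increased gut bacterial diversity, experience beneficial changes in microbiota composition". The other is functional: they are to "demonstrate decreased transcriptional activity of inflammatory pathways that have been previously correlated with an increased risk of colon cancer".

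**Direction of the expected shift.** Table 2 in Section 9.1.1.2 lists *F. nucleatum*, *E. coli* and *Akkermansia* as decreased by EPA and links them to inflammation or colorectal cancer. It gives directions, not sizes.

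**Design.** Section 13.1: "This study is a single-arm trial of EPA treatment in patients with a history of colorectal adenoma". The comparison is before versus after treatment.

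**The concern.** The quantity modelled and the conclusion expected from it are not the same. Community RNA for a pathway combines copy number with transcription per copy. The expected conclusion concerns activity, yet the trial's own hypothesis is that copy number will move too.

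If inflammation-linked organisms decline as Table 2 suggests, RNA from pathways they carry can fall with no change in how those pathways are transcribed. The shift would be in the hypothesised direction, so one compositional effect could be read a second time as a functional effect. The reverse can also happen: a real change in per-copy transcription can be hidden by an opposite change in abundance. A control arm would not solve this, because treatment could still act through either component. Separating them needs the matched DNA, which the trial already plans to sequence.

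**Working it through.** **1. The plan's own figure.** Section 13.2 states: "With 80% power and the significance level of 0.05 in a two-sided paired t-test, we will require 73 participants". That is for the primary endpoint, with a mean change of 3.0% and an SD of the paired difference of 9.0%. An exact noncentral-t calculation gives n = 73 with power 80.2%, which matches. With 10% dropout, 80 × 0.9 = 72 pairs (power 79.7%). The documents give no power, effect size or SD for the metatranscriptomic endpoint. The steps below borrow only the 72 pairs.

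**2. What the RNA model estimates.** Let taxon j carry D_j copies of a pathway and make a_j transcripts per copy. Then

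DNA = Σ D_j and RNA = Σ D_j·a_j.

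If all carriers have the same per-copy expression a, then RNA = a·DNA and

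Δlog2 RNA = Δlog2 DNA + Δlog2 a.

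With two visits and complete pairs, a mixed model with a participant intercept and a pre/post term estimates the mean of this sum. Without a DNA term it cannot return the two parts separately.

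**3. Illustration, a unchanged.**
- All carriers halve: log2(0.50) = −1.0.
- All carriers fall by 25%: log2(0.75) = −0.42.

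Subtracting the DNA change gives 0 in both cases, by construction.

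**4. How often the RNA model would signal.** Simulation with 20,000 replicates, 72 pairs, two-sided 0.05, one pathway and no change in per-copy activity. Assumed: SD of the paired log2 activity change 1.0; SD of the paired log2 DNA change 1.0, 1.5 or 2.0; normal and independent changes; DNA measured without error. Entries are the share of replicates with p < 0.05.

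| Fall in DNA | RNA only, DNA SD 1.0 | DNA SD 1.5 | DNA SD 2.0 |
|---|---|---|---|
| none | 5.1% | 4.8% | 5.3% |
| 20% | 48.1% | 31.7% | 22.6% |
| 33% | 92.9% | 77.0% | 58.3% |
| 50% | 100% | 99.7% | 96.2% |

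With log(RNA/DNA), or with the DNA change as a covariate, the share was 4.7% to 5.3% in every cell. An RNA-only signal is a true finding about community output. It is false only if read as a change per copy.

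**5. Reverse case.** DNA halved, per-copy activity doubled, both SDs 1.0: −1.0 + 1.0 = 0. The RNA-only test rejects in 4.9% of replicates and the DNA-corrected tests in 100%.

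**6. Limit of a community-level correction.** Let taxa A and B each carry 0.5 of the copies, with 5 and 1 transcripts per copy. A halves; neither changes its transcription.
- DNA: 0.5 + 0.5 = 1 becomes 0.25 + 0.5 = 0.75; log2(0.75) = −0.42.
- RNA: 2.5 + 0.5 = 3 becomes 1.25 + 0.5 = 1.75; log2(1.75/3) = −0.78.
- RNA/DNA: 3 becomes 1.75/0.75 = 2.33; log2(2.33/3) = −0.36.

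The community ratio removes 0.42 of the 0.78 and leaves −0.36. Within each species the ratio is unchanged (5 and 1), so the corrected change is 0. The bias equals the log DNA change only when carriers have equal per-copy expression.

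**The case against.** Several points on the other side are sound.

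- **Silence is not exclusion.** Section 13.6 lists no model terms beyond treatment status, and an unstated step in the cited software could normalise for DNA. Subsection 9.1.5.3 was not available here, so the absence of a correction is asserted only for the text that could be read. A reader might infer that the plan fits RNA on pre/post status and nothing else, and that compositional change will be reported as altered transcription. The documents do not support that: they leave the model unspecified, and the sentence on activity is an expectation, not a rule for making claims.
- **Community output is a legitimate target.** Less total RNA from an inflammatory pathway may matter to the host whatever its cause. Composition is also tested in the same paragraph, so a reader would see both results. This stands for RNA reported as output. It does not turn output into activity.
- **The sizes are assumed.** Table 2 gives no magnitudes, and Section 9.1.1.2 attributes these shifts to animal studies. A pathway carried by several taxa need not lose DNA when one taxon declines. Steps 3 to 5 show direction and range, not a forecast.
- **A simple ratio is not a complete cure.** Step 6 confirms this, and it shapes the fix.
- **DNA abundance is itself measured after treatment.** Adjusting for it changes the question from total effect to change at given abundance. That is the question a statement about activity asks, so both analyses should be shown.

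None of these removes the gap between the model as written and the stated conclusion.

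**Conclusion.** The concern holds in a limited form. As written, Section 13.6 does not identify the activity conclusion it anticipates: a fall in pathway RNA may reflect fewer carriers, less transcription per copy, or both.

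The size cannot be fixed from the documents. When carriers have equal per-copy expression, the error in an activity reading equals the log DNA change, for example −1.0 log2 if all carriers halve. When carriers differ it can be larger than the DNA change (−0.78 against −0.42 in the two-taxon example). Under the assumed SDs at 72 pairs, DNA falls of 20% to 50% make the RNA-only test significant in about 23% to 100% of replicates with no per-copy change.

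It does not follow that the RNA analysis is invalid or that a misleading report is certain. The matter affects one component of a secondary endpoint. The primary endpoint and N = 80 are untouched.

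**What to change.** In Section 13.6:

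1. Keep community RNA pathway abundance as a measure of total community output, and report it beside the matched DNA result for the same pathway.
2. Base any claim of altered transcriptional activity on one prespecified DNA-corrected mixed model: log RNA on treatment status, with matched log DNA from the same stool sample as a covariate and a participant term.
3. Fit it on species-stratified pathway abundances where these are detectable, with the community-level version as support.
4. State in advance how zero DNA is handled.

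The cost is analysis code and a few sentences in the plan; no new samples or assays are needed. There are three downsides. Features undetected in DNA drop out. Stratified data are sparser, so fewer pathways can be tested and with less precision. Noise in measured DNA flattens the covariate slope, so part of the compositional shift can remain in the corrected estimate.
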